7.1.2 Laboratory Tests

Clinical laboratory parameters (hematology, serum chemistry and electrolytes) will be evaluated.

Laboratory tests will be graded using the NCI Common Terminology Criteria, and the most recent version of the criteria at the time of the database lock will be used.

Clinical laboratory data will be first analyzed using International System of Units (SI).

Analyses will be repeated using US conventional units.

In the laboratory summary tables, unless otherwise specified, subjects will be counted only once for each lab parameter according to their worst on treatment CTC grade (worst being the highest CTC grade). The laboratory tables and listings will be sorted by laboratory category, laboratory subcategory and laboratory test code sequence number.

7.1.3 Immunogenicity data

Blood samples for immunogenicity analysis will be collected from subjects assigned to the experimental treatment group according to the protocol schedule. Samples will be evaluated for development of Anti-Drug Antibody (ADA) by a validated electrochemiluminescent (ECL) immunoassay.

7.2 Study Conduct

The Relevant Protocol Deviations will be summarized and listed based on all randomized subjects, by treatment group and overall.

The following programmable deviations from inclusion and exclusion criteria will be considered as relevant protocol deviations. Non-programmable relevant eligibility and on-treatment protocol deviations, as well as significant (both programmable and nonprogrammable) eligibility and on-treatment protocol deviations will be reported through ClinSIGHT listings.

At Entrance:

- Subjects who, at the time of the initial diagnosis, do not have histologically confirmed esophageal or gastroesophageal junction cancer; OR the stage at initial diagnosis is not Stage II or Stage III.
- Subjects who did not receive concurrent neo-adjuvant CRT prior to complete resection (i.e. they received only neo-adjuvant chemotherapy or only radiation or none prior to surgery).
- Subjects who received treatment directed against the resected GEJ or esophageal cancer (e.g., chemotherapy, targeted agents, radiation, or biologic therapy) that is administered after the complete resection.
- Subjects do not have residual disease (i.e. subjects who have ypN0 AND ypT0)
- Subjects who had complete resection > 18 weeks before randomization.
- Subject with baseline ECOG performance status > 1.
- Subjects who are not disease-free by imaging

On-study:

- Subjects receiving concurrent anti-cancer therapy (chemotherapy, hormonal therapy, immunotherapy, non-palliative radiation therapy, standard or investigational agents for treatment of EC or GEJ cancer).
- Subjects treated differently as randomized (subjects who received the wrong treatment, excluding the never treated).

A subject listing will also be produced.

Enrollment by country and site, and enrollment by month will be summarized and listed for all enrolled subjects.

A by-subject listing of batch numbers for all treated subjects will be provided.

7.3 Study Population

Analyses in this section will be tabulated for all randomized subjects by treatment group as randomized, unless otherwise specified.

7.3.1 Subject Disposition

The total number of subjects enrolled (randomized or not randomized) will be presented along with the reason for not being randomized. This analysis will be performed on the all enrolled subjects population only.

Number of subjects randomized but not treated along with the reason for not being treated will be tabulated by treatment group as randomized.

Number of subjects who discontinued study treatment along with corresponding reason will be tabulated by treatment group as treated. Reason for discontinuation will be derived from subject status CRF page. This analysis will be performed only on the all treated subjects population.

A by-subject listing for all treated subjects will be provided showing the subject's off treatment date and whether the subject continues in the study along with the reason for going off study. A by-subject listing for all enrolled subjects will also be provided, showing whether the subject was randomized along with the reason for not being randomized.

7.3.2 Demographics and Other Baseline Disease Characteristics

The following demographic and baseline disease characteristics will be summarized and listed by treatment group as randomized:

- Age (continuous)
- Age categorization (< 65, ≥ 65 and < 75, ≥ 75 and < 85, ≥ 85, ≥ 75, ≥ 65)
- Sex (Male vs. Female)
- Race (White, Black or African American, Asian, American Indian or Alaska Native, Native Hawaiian or Other Pacific Islander, Other)
- Region (US/Canada, Europe, Asia, Rest of the World [RoW])
- Baseline weight (descriptive statistics)
- Smoking status (current/former, never smoker, unknown)

- Baseline ECOG PS
- Disease at initial diagnosis (EC, GEJ cancer)
- Disease stage at initial diagnosis (Stage I, Stage II, Stage III, Stage IV)
- Disease at study entry (EC, GEJ cancer)
 - EC: body location (Lower third, middle third, upper third)
 - GEJ cancer: Siewert-Stein (Type I vs. Type II vs. Type III)
- Histology (adenocarcinoma, squamous cell carcinoma, other) (stratification factor: squamous vs. adenocarcinoma)
- Histological grade (G1, G2, G3, G4, GX)
- Pathologic TN classification at study entry
 - Tumor (ypT0, ypT1, ypT2, ypT3, ypT4, unknown)
 - Nodes (ypN0, ypN1, ypN2, ypN3, unknown) (stratification factor: ypN0 vs. ≥ ypN1)

- Time from complete resection to randomization (< 4 weeks, 4 - 10 weeks, < 10 - 16 weeks, > 16 weeks).
- Time from randomization to first dose date (≤ 3, 4 - 5, 6 - 7, 8 - 14, 15 - 21, > 21, Not Reported or Not Treated)

- HER-2 status at study entry (negative, positive, unknown)
- Microsatellite instability (MSI-H, MSI-L, MSI-S, unknown)
- EBV status (positive, negative, unknown)

- Baseline LDH (\leq ULN, $>$ ULN; $\leq 2*ULN$, $> 2*ULN$)
- Baseline hemoglobin ($<$ 10g/dL, \geq 10g/dL)

- Baseline PD-L1+ status based on a 1% cut off ($\geq 1\%$ vs. $< 1\%$ or indeterminate)
- Baseline PD-L1+ status based on a 5% cut off ($\geq 5\%$ vs. $< 5\%$ or indeterminate)
- Baseline PD-L1+ status based on a 10% cut off ($\geq 10\%$ vs. $< 10\%$ or indeterminate)

For the purposes of displaying baseline characteristics, stratification factors will be retrieved from the CRF.

7.3.3 Medical History

A by-subject listing of general medical history for all randomized subjects will be provided.

7.3.4 Prior Therapy Agents

Prior cancer therapy will be summarized by treatment group and overall.

Prior anti-cancer therapy:

- Setting of prior systemic therapy regimen received (adjuvant, metastatic disease, neo-adjuvant).
- Prior radiotherapy (yes or no).
- Time from beginning of neoadjuvant CRT to complete resection ($<$ 4weeks, 4-6 weeks, $<$ 6-8, $>$ 8weeks)
- Prior surgery related to cancer (yes or no)
 - type of surgery (esophagectomy, proximal gastrectomy, total gastrectomy, distal gastrectomy, d0, d1, d2, d3, three field lymph node dissection, other)
- Prior systemic therapy classified by therapeutic class and generic name.

Other Prior therapy:

- Prior/current non-study medication classified by anatomic and therapeutic classes.

Agents and medication will be reported using the generic name. A listing by subject will also be provided.

7.3.5 Physical Examinations

Subjects with abnormal baseline physical examination will be listed by subject.

7.3.6 Baseline Physical Measurements

Baseline physical measurements will be listed by subject.

7.3.7 Discrepancies between IWRS and CRF Stratification Factors

Summary tables (cross-tabulations) by treatment group for stratification factor will be provided to show any discrepancies between what was reported through IWRS vs. CRF data (baseline):

- 1) PD-L1 status ($\geq 1\%$ vs. $< 1\%$ or indeterminate) (IWRS vs. clinical database)
- 2) Pathologic lymph node status (positive \geq ypN1 vs. negative ypN0) (IWRS vs. CRF data)
- 3) Histology (squamous vs. adenocarcinoma) (IWRS vs. CRF data).

7.4 Extent of Exposure

Listings will include all available exposure data. Analyses will be performed by treatment group “as treated” in all treated subjects, unless otherwise specified.

7.4.1 Administration of Study Therapy

For this study, dosing schedule per protocol is as follows:

- 240mg every 2 weeks for 16 weeks (8 doses) [240mg dosing]
 - Note that a subject has to receive all 8 240mg doses before he/she starts on the 480mg doses. (Even if, due to dose delays, a patient would receive his/her 8th 240mg dose later than Week 16.)
- 480mg every 4 weeks beginning at Week 17 (2 weeks after the 8th dose) [480mg dosing]

The following parameters will be summarized (descriptive statistics) by treatment group:

- Number of doses received
- Cumulative dose
- Relative dose intensity (%) using the following categories: $< 50\%$; $50 - < 70\%$; $70 - < 90\%$; $90 - < 110\%$; $\geq 110\%$
- Duration of treatment

Duration of study therapy will be summarized (descriptive statistics) by treatment group.

Duration of study therapy will be calculated using a KM curve whereby the last dose date will be the event date for those subjects who are off study therapy. Subjects who are still on study therapy will be censored on their last dose date. Median duration of treatment and associated 95% CI will be provided.

A by-subject listing of dosing of study medication (record of study medication, infusion details, and dose changes) will be also provided.

Table 7.4-1: Administration of study therapy: definition of parameters

Nivolumab
Dosing schedule per protocol

Table 7.4-1: Administration of study therapy: definition of parameters

Nivolumab	
Dose	
  240mg dosing: ratio of Total Volume Infused with Total Volume Prepared x 240 in mg  480mg dosing: ratio of Total Volume Infused with Total Volume Prepared x 480 in mg 
Volume infused/prepared in mL at each dosing date is collected on the CRF.

Cumulative Dose	The sum of all doses (mg) administered to a subject during the treatment period
Relative dose intensity (%)	$100 \times \frac{\text{cumulative dose (mg)}}{(\text{Last dose date of nivo} - \text{first dose date of nivo} + X) \times \frac{120 \text{ (mg)}}{7 \text{ (days)}}$ 
X is 14 days if the last dose of nivolumab the patient plans to receive is 240mg; X is 28 days if the last dose of nivolumab the patient plans to receive received is 480mg.

Duration of study therapy	Last dose date - Start dose date + 1

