4.5 Selection and Timing of Dose for Each Subject

Table 4.5-1: Nivolumab (or placebo) dosing

Drug	Dose	Frequency of administration	Route of administration	Duration
Nivolumab (or placebo)	240 mg (or placebo) [Cycles 1-8]	Every 2 weeks, for 8 doses	Intravenous (IV) infusion	Until recurrence or discontinuation from study for a maximum of 1 year
	480 mg (or placebo) [Cycles 9-17]	Every 4 weeks starting at Cycle 9		

Subjects will receive treatment with nivolumab (BMS-936558) or placebo monotherapy. Subjects randomized to nivolumab will receive 240 mg nivolumab administered as an IV infusion over 30 minutes every 2 weeks for 16 weeks (8 doses) followed by 480 mg nivolumab administered as an IV infusion over 30 minutes every 4 weeks beginning at Week 17 (2 weeks after the 8th dose). Subjects randomized to placebo will receive placebo administered as an IV infusion over 30 minutes every 2 weeks for 16 weeks (8 doses) followed by placebo as an IV infusion over 30 minutes every 4 weeks beginning at Week 17 (2 weeks after the 8th dose). Treatment will be given until disease recurrence, unacceptable toxicity, or subject withdrawal of consent with a maximum of 1-year total duration of study medication.

First dose must be administered within 3 calendar days following randomization. There are no pre-medications recommended on the first cycle. If an acute infusion reaction is noted, subjects should be managed according to [Section 4.5.6](#). At the end of the infusion, flush the line with a sufficient quantity of diluent. Refer to drug preparation manual for more detail.

Dosing modifications:

There will be no dose modifications allowed for the management of toxicities of individual subjects. Subjects should be carefully monitored for infusion reactions during nivolumab administration. If an acute infusion reaction is noted, subjects should be managed according to [Section 4.5.6](#).

Doses of nivolumab may be interrupted, delayed, or discontinued depending on how well the subject tolerates the treatment. Dosing visits are not skipped, only delayed.

Dosing window:

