9 DOCUMENT HISTORY

Table 9-1: Document History

Version Number	Author(s)	Description
1.0 Apr 25, 2017		Original Issue based on revised protocol 01 dated Aug 24, 2016

Table 9-1: Document History

[figure not shown]
[figure not shown]

2.0 Oct 24, 2019
		
Based on revised protocol 03 dated June 06, 2019. The following changes are made in the SAP amendment to reflect the protocol amendment of having DFS as the primary endpoint, and OS as the secondary endpoint.  .
 
 • Objectives and endpoints to keep DFS as the sole primary endpoint and change OS to the secondary endpoint • Sample size and power • Schedule of analyses • The method to maintain blinding of OS if not positive at two interim looks of the studyThe method for alpha spending between IA and FA for DFS and OS PFS2 definition and analyses 
The SAP amendment also incorporates the IO core SAP.

3.0 May 4, 2020
		
Minor updates from SAP version 2.0 to add sensitivity analyses in Section 7.5.2.1 and other minor edits. Details are summarized below.
 
 • • Remove dose reduction in Section 7.6.4 as it is not applicable in this study. • Include in 7.5.2.2 Consistency of Treatment Effect in Subsets, Pathologic tumor status (ypT0, ypT1/ypT2, ypT3/ypT4, unknown) • Remove cumulative plot of baseline PD-L1 expression in section 7.8 as it is not very informative. • Remove the log-rank test and keep the Cox model for the subgroup analysis by PD-L1 status in section 7.8. • Add "c) no on-study disease assessment but death with prior subsequent therapy or second primary cancer" for censored on randomization date in section 7.5.2

4.0 Sept 30, 2020
		
Minor format update on hyperlinks, references, and page numbers. Correction of the relative dose intensity formula in Table 7.4-1 Administration of study therapy: definition of parameters.

Table 9-1: Document History

--	--	--

APPENDIX 1 TIME-TO ONSET AND TIME-TO RESOLUTION DEFINITION AND CONVENTIONS FOR SELECT ADVERSE EVENTS, IMMUNE-MEDIATED ADVERSE EVENTS AND EVENTS OF SPECIAL INTEREST

Time-to onset definition

Time-to onset of AE (any grade) for a specific category is defined as the time between the day of the first dose of study treatment and the onset date of the earliest AE (of any grade) in this category.

The time-to onset of AE (grade 3-5) for a specific category is defined similarly with an onset date corresponding to a grade 3-5 AE.

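### SAP Table 7.4-1 ties X in the relative dose intensity formula to a planned dose; read literally, subjects dosed exactly on schedule who stop in Cycles 1-8 score 50.0-88.9% instead of 100%

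*SAP*

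**What the plan says.** SAP section 7.4.1 gives the dosing plan in two parts: "240mg every 2 weeks for 16 weeks (8 doses) [240mg dosing" and then "480mg every 4 weeks beginning at Week 17 (2 weeks after the 8th dose) [480mg dosing". It adds that all eight 240 mg doses come before any 480 mg dose. Protocol Table 4.5-1 has the same plan, with the later part given as "480 mg (or placebo) [Cycles 9-17".

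Table 7.4-1 then defines the exposure parameters:

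- Cumulative dose is "The sum of all doses (mg) administered to a subject during the treatment period".
- RDI is 100 times cumulative dose, divided by the days from first to last dose plus X, times 120 mg per 7 days.
- X has two branches. The first is "X is 14 days if the last dose of nivolumab the patient plans to receive is 240mg". The second is "X is 28 days if the last dose of nivolumab the patient plans to receive received is 480mg".

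RDI is reported by treatment group in five bands: below 50%, 50 to below 70%, 70 to below 90%, 90 to below 110%, and 110% or more.

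The document history (SAP section 9) lists under version 4.0: "Correction of the relative dose intensity formula in Table 7.4-1". It does not say what was changed.

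**The concern.** The span from first to last dose leaves out the period that the last dose itself covers, and X adds it back. That period is 14 days after a 240 mg dose and 28 days after a 480 mg dose, so X should depend on the last dose given. The SAP makes it depend on a planned dose and does not define the term. The second branch leaves two wordings side by side, so the two branches do not clearly follow one rule, and a programmer must guess.

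A wrong choice falls only on subjects who stop in Cycles 1-8, including any who stop for early toxicity. They would appear under-dosed after receiving every scheduled dose on time. If early stopping differed between arms, the RDI bands would differ partly for an arithmetic reason.

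**Working it through.** **Inputs.** 240 mg every 14 days for eight doses (days 0 to 98), then 480 mg every 28 days from day 112 through Cycle 17 (SAP 7.4.1; Protocol Table 4.5-1). The formula and the values of X are from SAP Table 7.4-1. The dosing window for Cycles 1-8 is from Protocol section 4.5: up to 2 days early or 3 days late, and at least 12 days after the previous dose.

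**The plan's own figure.** 240/14 × 7 = 120 mg per week and 480/28 × 7 = 120 mg per week, so the 120 mg per 7 days in the denominator is right for both phases.

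**Full course.** Dose: 8 × 240 + 9 × 480 = 6240 mg. Span: 112 + 8 × 28 = 336 days. With X = 28 the denominator is (336 + 28) × 120/7 = 6240 mg, so RDI = 100%. For stops after any of doses 9 to 17 on schedule, X = 28 also gives 100%.

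**Stops after n = 1 to 8 doses at exact 14-day intervals.** The numerator is 240n mg and the span is 14(n − 1) days.

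- X = 14: denominator (14(n − 1) + 14) × 120/7 = 240n mg, so RDI = 100% for every n.
- X = 28: denominator (14(n − 1) + 28) × 120/7 = 240(n + 1) mg, so RDI = n/(n + 1).

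| Doses given | Cumulative dose (mg) | Span (days) | RDI, X = 14 | RDI, X = 28 |
|---|---|---|---|---|
| 1 | 240 | 0 | 100.0% | 50.0% |
| 2 | 480 | 14 | 100.0% | 66.7% |
| 3 | 720 | 28 | 100.0% | 75.0% |
| 4 | 960 | 42 | 100.0% | 80.0% |
| 5 | 1200 | 56 | 100.0% | 83.3% |
| 6 | 1440 | 70 | 100.0% | 85.7% |
| 7 | 1680 | 84 | 100.0% | 87.5% |
| 8 | 1920 | 98 | 100.0% | 88.9% |

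With X = 28, one or two doses fall in the 50 to below 70% band, and three to eight doses in the 70 to below 90% band.

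**Three readings of the clause.**

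1. *Last dose of the planned course.* This is 480 mg for every subject, so X = 28 always, the 14-day branch never applies, and the last column holds.
2. *Next planned dose.* After doses 1 to 7 the next dose is 240 mg, X = 14, and RDI is 100%. After dose 8 the next dose is 480 mg, X = 28, and RDI = 1920/2160 = 88.9%.
3. *Scheduled level of the last dose given.* X = 14 after any 240 mg dose and X = 28 after any 480 mg dose. RDI is 100% after any of doses 1 to 17.

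**Effect of the dosing window with X = 28.** If dose 8 is given 2 days early, RDI = 1920 / ((96 + 28) × 120/7) = 1920/2125.7 = 90.3%. One day early gives 89.6%; 3 days late gives 86.8%. As an extreme, if every gap were 12 days, doses 5 to 8 would give 92.1, 95.5, 98.0 and 100.0%. With X = 14 the same subjects would score 112.9, 113.5, 114.0 and 114.3%, so the downward shift remains.

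**The case against.** The best defence is that reading 3 was intended, and much supports it. A reading that empties one of two written branches is unlikely to be what the authors meant. The formula is anchored on the date of the last nivolumab dose, which is the dose given. The same table prorates each dose by volume infused over volume prepared, so the amount received can be less than 240 or 480 mg; a reference to the planned level of that dose would then make sense. SAP section 7.4.2.1 also keys 14 and 28 days to the 240 mg and 480 mg dosing phases. All of this stands as evidence of intent. It does not repair the sentence, which names a planned last dose and never mentions the scheduled level of a dose already given.

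A reader might infer that every compliant subject who stops in Cycles 1-8 is certain to score below 90%. The documents do not support that. It treats one reading as fact, and even with X = 28 a subject whose eighth dose is given 2 days early, within the permitted window, scores 90.3%.

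A reader might also infer from the version 4.0 entry that the literal rule was chosen deliberately. The entry records a correction without its content, so it shows nothing about intent. The doubled wording could be an edit left unresolved or struck-through text lost when the PDF was read.

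Finally, RDI is descriptive. Number of doses, cumulative dose, treatment duration and dose delays are reported beside it, so on-time early stoppers could be recognised there. Exposure-adjusted adverse event rates use their own exposure definition (SAP section 7.1.1). This limits the harm but does not make a wrong RDI right.

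**Conclusion.** The point holds as a defect of wording with a measurable effect under two of three readings. The arithmetic of the formula is sound once X is set correctly. On the literal reading, subjects dosed at exact 14-day intervals who stop after 1 to 8 doses score 50.0% to 88.9% instead of 100%, slightly higher if dosed early within the window. On the next-dose reading only stops after dose 8 are wrong, at 88.9%. On the probable intended reading nothing is wrong. Subjects who reach 480 mg are unaffected on schedule.

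The effect on the arm summaries cannot be sized from the documents, which give no share of subjects stopping in Cycles 1-8. If that share were 10 to 25% (an assumption, for illustration only), up to 10 to 25 percentage points of an arm would leave the 90 to below 110% band under the literal reading. A difference between arms is possible but hypothetical. No efficacy test, alpha or power is touched. Low severity.

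**What to change.** Replace both clauses for X in Table 7.4-1 with one rule:

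*X = 14 days if the last dose administered was at the scheduled 240 mg level (Cycles 1-8); X = 28 days if it was at the scheduled 480 mg level (Cycles 9-17), regardless of whether the infusion was complete.*

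The closing words keep the useful part of the planned-dose idea: an incomplete infusion does not change X. The cost is one sentence in the SAP and one programming condition. If the table has already been programmed, confirm which rule the program uses and re-run the RDI summary only if it differs.

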7.4.2 Modifications of Study Therapy

7.4.2.1 Dose Delays

Per protocol, a dose will be considered as actually delayed if the delay is exceeding 3 days. The maximum delay allowed between doses (for both nivolumab and placebo) is 42 days. Dose delay is defined as follows:

- 240mg dosing: duration of preceding cycle in days - 14
- 480mg dosing: duration of preceding cycle in days - 28

Dose delays will be divided into following categories: on-time, 4 - 7 days, 8 - 14 days, 15 - 42 days, 43 - 70 days, > 70 days. Reason for dose delay will be retrieved from CRF dosing pages.

The following parameters will be summarized by treatment arm:

- Number of dose delayed per subject, Length of Delay and Reason for Dose Delay.

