For Cycles 1-8, subjects may have study drug administered up to 2 days before or 3 days after the scheduled dosing date. Subjects may be dosed no less than 12 days from the previous dose. For Cycles 9-17, subjects may be dosed within a +/- 3 day window. A maximum delay of 6 weeks (42 days) between doses of nivolumab (or placebo) during Cycles 1-8 or a maximum delay of 10 weeks (70 days) between doses of nivolumab (or placebo) during Cycles 9-17 are allowed.

4.5.1 *Antiemetic Premedications*

Antiemetic premedications should not be routinely administered prior to dosing of drugs. See [Section 4.5.6](#) for premedication recommendations following a nivolumab related infusion reaction.

4.5.2 *Dose Delay Criteria*

Dose delay criteria apply for all drug-related adverse events. Treatment delays up to 6 weeks (42 days) from the last dose of nivolumab (or placebo) during Cycles 1-8 or up to 10 weeks (70 days) from the last dose of nivolumab (or placebo) during Cycles 9-17 are allowed.

Nivolumab (or placebo) administration should be delayed for the following:

- Any Grade \geq 2 non-skin, drug-related adverse event, with the following exceptions:
 - Grade 2 drug-related fatigue does not require a treatment delay
- Grade 2 drug-related creatinine, AST, ALT or Total Bilirubin abnormalities
- Any Grade 3 skin, drug-related adverse event
- Any Grade 3 drug-related laboratory abnormality (excluding AST, ALT or Total Bilirubin), with the following exceptions for lymphopenia, and asymptomatic amylase or lipase:
 - Grade 3 lymphopenia does not require dose delay
 - Any Grade \geq 3 drug-related amylase or lipase abnormalities that is not associated with symptoms or clinical manifestations of pancreatitis do not require a dose delay.
- Any adverse event, laboratory abnormality, or intercurrent illness which, in the judgment of the investigator, warrants delaying the dose of study medication.

Subjects who require delay of nivolumab should be re-evaluated weekly or more frequently if clinically indicated and resume nivolumab dosing when re-treatment criteria are met.

Note: per BMS standards, the term “interruption” is reserved for interruption of the actual IV infusion during administration. The terms omission and interruption should not be used synonymously when completing the CRF forms.

4.5.2.1 *Adverse Event Management Algorithms for Immuno-Oncology Agents*

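### SAP 7.4.2.1 gives one 42-day maximum dose delay where the protocol gives two limits, and its 15-42 day band cannot show over-limit delays in Cycles 1-8

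*SAP*

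**What the plan says.** **SAP 7.4.2.1 (Dose Delays)** makes four statements that matter here.

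- A threshold: "Per protocol, a dose will be considered as actually delayed if the delay is exceeding 3 days".
- A maximum, in the next sentence: "The maximum delay allowed between doses (for both nivolumab and placebo) is 42 days".
- A definition of delay by dosing phase. The first line reads "240mg dosing: duration of preceding cycle in days - 14"; the 480 mg line is the same with 28 subtracted.
- One set of bands for both phases: "on-time, 4 - 7 days, 8 - 14 days, 15 - 42 days, 43 - 70 days, > 70 days".

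The number of delayed doses, the length of delay and the reason are then summarised by treatment arm.

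**Protocol 4.5**, under the dosing window, gives two limits. The one for the 240 mg phase is 42 days. The one for the 480 mg phase is longer: "a maximum delay of 10 weeks (70 days) between doses of nivolumab (or placebo) during Cycles 9-17 are allowed".

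**Protocol 4.5.2** has the same two figures and fixes the starting point. For the 240 mg phase it reads "Treatment delays up to 6 weeks (42 days) from the last dose of nivolumab (or placebo) during Cycles 1-8". The 70-day figure for the 480 mg phase is counted in the same way. Protocol 4.5.4 and 4.5.5 repeat both figures, counted from the last dose, as the point beyond which treatment is permanently discontinued, subject to exceptions.

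The SAP's own table of protocol amendments (Table 2.4-1, Amendment 06) also records 42 days for Cycles 1-8 and 70 days for Cycles 9-17.

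**The concern.** There are two separate problems. First, the SAP states one maximum where the current protocol has two, and does not say whether its 42 days is an interval since the last dose or a delay on its own scale. Second, the band edges at 42 and 70 carry the protocol's numbers but are applied to a quantity from which 14 or 28 days have already been subtracted. Someone reading the table would naturally take those edges to mark the protocol limits.

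What is at stake is modest but practical. Passing the limit leads to discontinuation unless an exception applies, and the medical monitor must be consulted before dosing restarts. A delay table should be able to show how often that point was passed. No other planned summary gives the count directly: dose delay is not among the programmable relevant deviations in SAP 7.2.

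**Working it through.** **Inputs**

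- Protocol limits, in days since the last dose: 42 (Cycles 1-8) and 70 (Cycles 9-17), from Protocol 4.5.2, 4.5.4 and 4.5.5.
- Planned intervals: 14 days at 240 mg and 28 days at 480 mg.
- SAP delay = interval since the last dose - planned interval (SAP 7.4.2.1).
- SAP single maximum: 42 days.

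**Step 1. Can the SAP's 42 days be matched to the protocol?**

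| Reading of the SAP's 42 days | Cycles 1-8 | Cycles 9-17 |
|---|---|---|
| Interval since the last dose | 42 days, agrees | 42 against 70 days, conflicts |
| Delay on the SAP scale | 42 + 14 = 56 days since the last dose, 14 past the protocol's 42 | 42 + 28 = 70 days, agrees |

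Each reading matches one dosing phase and contradicts the other.

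**Step 2. Protocol limits on the SAP scale**

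- Cycles 1-8: 42 - 14 = 28 days.
- Cycles 9-17: 70 - 28 = 42 days.

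**Step 3. What each band contains**

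| SAP band (days of delay) | Cycles 1-8: interval, status | Cycles 9-17: interval, status |
|---|---|---|
| On-time (0-3) | 14-17, within | 28-31, within |
| 4-7 | 18-21, within | 32-35, within |
| 8-14 | 22-28, within | 36-42, within |
| 15-42 | **29-42 within; 43-56 over** | 43-70, within |
| 43-70 | 57-84, over | 71-98, over |
| >70 | 85 or more, over | 99 or more, over |

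Only one cell is mixed. In Cycles 1-8 the 28-day limit falls inside the 15-42 band. In Cycles 9-17 the limit falls exactly on the band edge. A count of over-limit delays taken from the two longest bands would therefore be complete for Cycles 9-17, but would omit every Cycle 1-8 interval of 43-56 days.

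**Step 4. A related gap at the switch of dose.** Cycle 9 is planned two weeks after dose 8. If the 480 mg formula applies to the dose being given, an on-time Cycle 9 dose has a delay of 14 - 28 = -14 days. If the formula follows the preceding cycle, the delay is 14 - 14 = 0. The SAP does not say which offset applies.

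**The case against.** Several points on the other side have force.

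- **The bands work in Cycles 9-17.** A reader might infer that 480 mg intervals of 71-98 days are misclassified because they fall in the 43-70 band. They are not: every delay in that band is over the limit, and none shares a band with a delay within it. What remains is a labelling risk, that someone takes the upper edge of that band for the protocol's 70 days.
- **The table does not call any delay allowed.** A reader might infer that over-limit delays would be presented as permitted. The SAP attaches no such label and defines no over-limit flag; it summarises length and reason. The fault is that the 15-42 band is uninformative about the limit in Cycles 1-8.
- **Over the limit is not the same as a violation.** Protocol 4.5.5 allows longer delays for prolonged steroid tapers and, with the medical monitor's approval, for reasons unrelated to the drug. A new cut point would count delays past the limit, not breaches; the reason data are still needed.
- **Some subjects would not appear in any case.** The delay is computed from the preceding cycle's duration, which appears to need a later dose. A subject who stops permanently at the limit would contribute no such delay, and discontinuations are tabulated separately in SAP 7.3.1.
- **The SAP does not literally attribute the 42 days to the protocol.** The words per protocol open the preceding sentence, on the 3-day threshold, and reach the maximum only by context. Even so, a maximum that is allowed can hardly describe anything but a protocol rule.
- **The protocol's word delay could mean days beyond schedule.** Protocol 4.5 alone might be read so, and then the edges at 42 and 70 would sit on the limits. Protocol 4.5.2, 4.5.4 and 4.5.5 count from the last dose, so that reading does not survive. It would not rescue the single 42-day figure for Cycles 9-17 either.
- **The data are not lost.** The by-subject dosing listing in SAP 7.4.1 lets intervals be recovered.

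These points narrow the finding to one conflicting sentence and one mixed band. They do not remove either.

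**Conclusion.** The point holds in this limited form. The single maximum in SAP 7.4.2.1 conflicts with the current protocol text on any reading, and it is also out of line with the amendment history that the SAP itself reports. It may be a leftover: SAP version 1.0 was based on Revised Protocol 01, and the two-limit rule came with Amendment 06. That is inference, not something the documents state.

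The effect on the table is 14 days wide and sits in one phase: 240 mg intervals of 43 to 56 days cannot be told apart from those of 29 to 42. How many doses this concerns cannot be judged from the documents. If the two phases are pooled, which the SAP neither requires nor rules out, the same band also takes in 480 mg intervals of 43-70 days, all within their limit, and is harder still to interpret.

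The conclusion assumes that the protocol limits run from the last dose and that the SAP formula is applied in whole days. It takes no view on which limit is clinically right. The impact is confined to descriptive exposure reporting; the efficacy analyses, alpha, power and the programmable deviations do not depend on it. It is a minor correction.

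**What to change.** 1. Reconcile the maximum-delay sentence in SAP 7.4.2.1 with Protocol 4.5, 4.5.2, 4.5.4 and 4.5.5 and with the Amendment 06 entry in SAP Table 2.4-1.
2. State whether the limit and the bands are in days since the last dose or days beyond the planned interval, and use one scale for both.
3. Tabulate delays separately for 240 mg and 480 mg dosing, with a cut at each reconciled limit. If the protocol figures stand and the SAP scale is kept, this splits the 240 mg band into 15-28 and 29-42 days; the 480 mg bands need no change. Banding the interval since the last dose, with cuts at 42 days (Cycles 1-8) and 70 days (Cycles 9-17), would serve equally well.
4. Say which offset applies to the Cycle 9 dose.
5. Add a footnote that delays past the limit may fall under the exceptions in Protocol 4.5.5 and should be read with the recorded reason.

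The cost is a few sentences of SAP text and one table shell. No new data are needed, since dosing dates and reasons for delay are already collected.
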